1.3. Schedule of Activities (SoA)

The Schedules of Activities (SoA) are presented in the following [Table 1](#).

CONFIDENTIAL

[figure not shown]
[figure not shown]
221781
Protocol Final

Table 1 Schedule of Activities

Visit	Screening	Treatment Period 1				Washout	Treatment Period 2				Follow up or early withdrawal
Visit Window	Day -21 to Day-7	Day -1	Day 1 to Day 6	Day 7	Day 8	7 days \pm 2 days	Day -1	Day 1 to Day 6	Day 7	Day 8	8 days \pm 2 days after last TP (discharge)
Confinement ^a		X	X	X	X		X	X	X	X	
Admission		X					X				
Discharge from site					X					X	
Informed Consent	X										
Inclusion and exclusion criteria	X	X					X				
Demography	X										
Physical examination ^b	X										X
Body weight	X										
Height and BMI calculation	X										
Medical history (includes substance usage)	X										
Pulmonary tests ^c	X	X			X		X			X	
FSH	X										
Serology (HBsAg, anti-HCV, anti-HIV 1 and 2)	X										

CONFIDENTIAL

221781
Protocol Final

Visit	Screening	Treatment Period 1				Washout	Treatment Period 2				Follow up or early withdrawal
Visit Window	Day -21 to Day-7	Day -1	Day 1 to Day 6	Day 7	Day 8	7 days \pm 2 days	Day -1	Day 1 to Day 6	Day 7	Day 8	8 days \pm 2 days after last TP (discharge)
Drug and alcohol screen, cotinine test	X	X					X				
Clinical laboratory assessments ^d	X			X					X		X
Vital signs ^e	X	X	X	X	X		X	X	X	X	X
12-lead ECG ^f	X	X	X	X			X	X	X		X
MDI training ^g	X										
Randomization		X									
Randomization criteria ^h		X					X				
Administration of study intervention (propellants) ⁱ			X	X				X	X		
⁵⁷ Co transmission scan ^j			X								
Inhalation training ^k (saline without ^{99m} Tc)				X					X		
Nebulized ^{99m} Tc administration and percent radiolabeled particle retention measurements ^l				X					X		

CONFIDENTIAL

221781
Protocol Final

Visit	Screening	Treatment Period 1				Washout	Treatment Period 2				Follow up or early withdrawal
Visit Window	Day -21 to Day-7	Day -1	Day 1 to Day 6	Day 7	Day 8	7 days \pm 2 days	Day -1	Day 1 to Day 6	Day 7	Day 8	8 days \pm 2 days after last TP (discharge)
AE review ^m			←								→
SAE review ⁿ	←										→
Concomitant medication review	X	X	X	X			X	X	X		X

- Participants will be in the clinic for 2 periods, from Day -1 until Day 8; they will be discharged from site on Day 8, 24 h after nebulized 99mTc in both TP 1 and TP 2.

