5.1. Inclusion Criteria

Participants are eligible to be included in the study only if all following criteria apply:

1. Sex: male or female.
2. Age: 30 to 55 years, inclusive, at screening
3. BMI: 18.0 to 32.0 kg/m², inclusive, at screening
4. Weight: ≥50 kg
5. Nonsmokers or ex-smokers for more than 6 months with a smoking history of <10 pack years
6. Status: healthy participants
7. Spirometry data;
 - FEV1 ≥ 80% of predicted values;
 - FEV1:FVC ratio > 70%.
8. Females must be of nonchildbearing potential, as defined in Section [10.4.1.2](#).
9. A female participant is eligible to participate if:
 - She is a WONCBP, as defined in Section [10.4](#).
 - She agrees not to donate eggs (ova, oocytes) for the purpose of reproduction during the study intervention period and at least 30 days after the last dose of study intervention. She must also not be involved in the process of donating eggs prior to consenting to the study.
10. Male participants are eligible to participate if they agree to the following during the study intervention period and for at least 90 days after the last dose of study intervention:
 - Refrain from donating sperm

- Either be abstinent from heterosexual intercourse as their preferred and usual lifestyle (abstinent on a long term and persistent basis) and agree to remain abstinent
 - Or must agree to use a male condom when having sexual intercourse with a WOCBP who is not currently pregnant. The female partner should additionally use a highly effective contraceptive method with a failure rate of <1% per year as described in Section 10.4.
11. All prescribed medication must have been stopped at least 30 days prior to admission to the clinical research center based on investigator judgment (see Section 6.9). An exception is made for HRT, and occasional paracetamol which may be used throughout the study.
 12. Ability and willingness to abstain from alcohol from 48 hours (2 days) prior to screening, and from 48 hours (2 days) prior to each admission until discharge from the clinical research center at each study period.
 13. Ability and willingness to abstain from methylxanthine-containing beverages or food (coffee, tea, cola, chocolate, energy drinks) from 48 hours (2 days) prior to each admission to the clinical research center at each study period.
 14. Good physical and mental health on the basis of medical history, physical examination, clinical laboratory, ECG, and vital signs, as judged by the investigator.

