 15. Capable of giving written informed consent which includes compliance with the requirements and restrictions listed in the ICF and in this protocol.
 16. Capable of using inhaler device with no physical or other issues which would impair the participant's ability to successfully use a pMDI inhaler as instructed in this study.
 17. Ability to comply with the protocol. Subjects have capacity and no issues which would impair their ability to comply with all aspects of the protocol during the study.

The investigator is responsible for review of medical history, menstrual history, and recent sexual activity to decrease the risk for inclusion of a woman with an early undetected pregnancy.

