8.3.6. Pregnancy Testing

Not applicable, as only women of nonchildbearing potential (WONCBP) are eligible to participate in the study.

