10.2. Appendix 2: Clinical laboratory tests

- The clinical safety laboratory tests detailed in [Table 9](#) will be performed by the local laboratory.
- Protocol-specific requirements for inclusion or exclusion of participants are detailed in [Section 5](#) of the protocol.
- Additional tests may be performed at any time during the study as determined necessary by the investigator or required by local regulations.
- Investigators must document their review of each laboratory safety report.

Table 9 Protocol-required safety laboratory tests

Laboratory Tests	Parameters	
Hematology	
 • Platelet count 	
	
 • Red blood cell (RBC) count 	
	RBC indices	
 • Mean corpuscular volume (MCV) • Mean corpuscular hemoglobin (MCH) • %Reticulocytes
	Absolute WBC count with differential:	
 • Neutrophils • Lymphocytes • Monocytes • Eosinophils • Basophils
	
 • Hemoglobin 	
	
 • Hematocrit 	
Clinical chemistry¹	
 • Urea • Potassium • Creatinine* • Sodium • Calcium • Glucose fasting • Creatine phosphokinase (CPK) 	
 • Aspartate aminotransferase (AST)/serum glutamic-oxaloacetic transaminase (SGOT)¹ • Alanine aminotransferase (ALT)/serum glutamic-pyruvic transaminase (SGPT)¹ • Alkaline phosphatase² • Total bilirubin¹ • Direct bilirubin, only if total bilirubin is elevated • Total protein
Routine urinalysis	
 • Specific gravity • pH, glucose, protein, blood, ketones, [bilirubin, urobilinogen, nitrite, leukocyte esterase] by dipstick • Microscopic examination. Please note, this will only be performed if there is an abnormality in accordance with Clinical Laboratory standard procedures at investigator discretion. • Culture at investigator discretion (if positive: specify pathogen) 	
Other screening tests	
 • FSH and estradiol (as needed in WONCBP only) • Cotinine, alcohol and drug screen (to include at minimum: amphetamines [including XTC], methadone, barbiturates, cocaine, opiates, cannabinoids and benzodiazepines) • Serology [(HIV antibody 1/2 antibody test, hepatitis B surface antigen [HBsAg], and hepatitis C virus antibody)] • Testing for SARS-CoV-2 may be performed at the discretion of the physician and based on local guidelines. 	

NOTES

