10.4. Appendix 4: Contraceptive and barrier guidance

10.4.1. Definitions

10.4.1.1. Woman of Childbearing Potential (WOCBP)

Women in the following categories are considered WOCBP (fertile):

- Adolescents of childbearing potential: Tanner stage ≥ 2 (post-thelarche) irrespective of the occurrence of menarche or following menarche.
- From the time of menarche until becoming postmenopausal unless permanently sterile (see below)

Note: Menarche is the first onset of menses in a young female. Menarche is normally preceded by several changes associated with puberty including breast development and pubic hair growth.

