10.4.1.2. Woman of Nonchildbearing Potential (WONCBP)

Women in the following categories are considered WONCBP:

- Permanently sterile due to one of the following procedures:
 - a. Documented hysterectomy

- b. Documented bilateral salpingectomy
- c. Documented bilateral oophorectomy

For permanently sterile individuals due to an alternate medical cause other than the above, (e.g., Mullerian agenesis, androgen insensitivity, gonadal dysgenesis), investigator discretion should be applied to determining study entry. If reproductive status is questionable, additional evaluation should be considered.

Note: Documentation can come from the site personnel's review of the participant's medical records, medical examination, or medical history interview.

- **Postmenopausal female**

A postmenopausal state is defined as no menses for 12 months without an alternative medical cause.

- A high FSH level in the postmenopausal range may be used to confirm a postmenopausal state in women not using hormonal contraception or (HRT). However, in the absence of 12 months of amenorrhea, confirmation with more than 1 FSH measurement is required.
- Females on HRT and whose menopausal status is in doubt must discontinue HRT to allow confirmation of postmenopausal status before study enrollment.

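### A woman with less than 12 months of amenorrhea can enter as nonchildbearing on repeated FSH, and no pregnancy test is scheduled before either 99mTc dose: a small gap that is cheap to close

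*Protocol*

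**What the plan says.** Inclusion criterion 8 (Protocol 5.1) reads "Females must be of nonchildbearing potential, as defined in Section" 10.4.1.2, so everything turns on that definition.

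- **Who counts as childbearing.** Protocol 10.4.1.1 includes women "From the time of menarche until becoming postmenopausal unless permanently sterile".
- **Who counts as postmenopausal.** Protocol 10.4.1.2 says: "A postmenopausal state is defined as no menses for 12 months without an alternative medical cause". It then lets a high FSH support that status in women who take neither hormonal contraception nor HRT, and continues: "However, in the absence of 12 months of amenorrhea, confirmation with more than 1 FSH measurement is required".
- **Pregnancy testing.** Protocol 8.3.6 says: "Not applicable, as only women of nonchildbearing potential (WONCBP) are eligible to participate in the study".
- **Scheduled tests.** The Schedule of Activities (1.3) marks FSH at screening and has no pregnancy-test row. Table 9 (10.2) lists FSH and estradiol as needed, and no pregnancy test.
- **Safeguards.** After the inclusion criteria, Protocol 5.1 states: "The investigator is responsible for review of medical history, menstrual history, and recent sexual activity", with the aim of not including a woman whose pregnancy is early and not yet detected. Section 10.2 allows additional tests when the investigator finds them necessary or local regulations require them.
- **Why these women are excluded.** Table 2 in Section 2.2.1 and Section 2.2.3 both give the radiation exposure as the reason.

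**The concern.** Section 8.3.6 treats nonchildbearing status as a sufficient reason to plan no pregnancy test. That is sound for a woman who is surgically sterile or has had 12 months of amenorrhea. It is weaker for a woman who has menstruated within the past year and qualifies on FSH alone, because she is the least certain member of the eligible group.

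What is at stake is participant safety. The exclusion exists to keep possibly pregnant women away from the radiation. By this route, that protection rests on FSH results, a history review and tests that the investigator may or may not order.

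**Working it through.** The claim concerns what is and is not scheduled, so the main check is to set the sections side by side. The arithmetic only gives context.

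**1. Does the route exist?** Under 10.4.1.1 a woman stays of childbearing potential until she is postmenopausal or permanently sterile. The definition in 10.4.1.2 requires 12 months without menses. Its FSH bullet then deals with women who lack those 12 months and asks for more than one FSH. It sets no minimum amenorrhea and no spacing between measurements. Criterion 8 imports all of this. The route exists.

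**2. Is a pregnancy test scheduled before either 99mTc dose?**

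| Place | Pregnancy test planned? |
|---|---|
| Protocol 8.3.6 | No, declared not applicable |
| Schedule of Activities: screening, Day -1 and Day 7 of both periods | No row |
| Table 9, other screening tests | None listed |
| SAP Table 2 | None listed |

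**3. What else protects these women?**

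| Safeguard | Source | A planned objective check? |
|---|---|---|
| Review of menstrual history and recent sexual activity | 5.1 | No, but aimed at undetected pregnancy |
| Additional tests, by discretion or local rule | 10.2 | Permitted, not scheduled |
| Eligibility rechecked on Day -1 of both periods | 1.3 | No |
| Health-status change reviewed at the start of both periods | 5.3 | No |
| Confinement from Day -1 to Day 8 | 1.3: "Participants will be in the clinic for 2 periods, from Day -1 until Day 8" | No |
| Withdrawal at the investigator's discretion | 7.2 | No |

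The contraception guidance in 10.4.2 addresses partners of male participants. Criterion 9 asks female participants for nonchildbearing status and no egg donation, not for contraception.

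**4. Radiation figures (Protocol 10.9).** The plan's own totals reproduce:

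- Per administration: 0.5 + 2 × 0.03 = 0.56 mSv
- Period 1, with one 57Co scan: 0.56 + 0.1 = 0.66 mSv
- Total: 2 × 0.56 + 0.1 = 1.22 mSv
- Maximum, with two repeat scans: 1.22 + 2 × 0.1 = 1.42 mSv

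These are effective doses to the participant. They are not fetal doses.

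**5. Timing.** Screening falls on Day -21 to Day -7. With no Day 0, that is 13 to 27 days before the first 99mTc dose on Day 7. It is about 25 to 44 days before the second, depending on whether the 5 to 9 day washout is counted to Day 1 or to Day -1 of Period 2. These counts show how old the screening information can be. They do not bound the risk, because an unrecognised pregnancy could predate screening.

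**6. Size.** The documents give neither the number of women who would use the route nor their chance of pregnancy. The number could be 0 of 24. No risk can be calculated.

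**The case against.** The strongest reply is that this is a deliberate eligibility choice. The quoted FSH sentence is itself a tightening, since it asks for more than one measurement, and Section 8.3.6 follows logically from who is eligible. The history review names the very risk at issue. Section 10.2 allows a pregnancy test whenever the investigator or local regulations call for one. The study runs under ionising-radiation medical exposure regulations, with ARSAC approval and practitioner review (10.1.1). A check may therefore happen in practice.

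Much of this stands, and it rules out three stronger readings:

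- **That the protocol ignores undetected pregnancy, or acts only on a known one.** The review in 5.1 is aimed at undetected pregnancy.
- **That the repeat FSH cannot be done because only one draw is scheduled.** The schedule marks FSH at a screening visit with a two-week window and does not limit it to one draw. Table 9 allows it as needed.
- **That the site will do no pregnancy check.** The regulatory and ARSAC requirements are not reproduced, so the documents do not settle this.

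What the reply does not supply is a planned objective check. Each safeguard depends on history, judgement or rules outside the protocol, and no rationale is given for using the FSH route without a test in a radiation study.

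**Conclusion.** The point holds as a minor, avoidable gap in participant protection. As written, a woman with less than 12 months of amenorrhea can receive both 99mTc doses and the 57Co scan with no scheduled pregnancy test, although women of childbearing potential are excluded because of that radiation.

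The residual risk is small: repeated FSH in the postmenopausal range is required, history is reviewed, participants are confined before each dose, and few women, possibly none, would use the route. A reader might take the day counts or the 1.22 to 1.42 mSv as a measure of the risk. They are not, for the reasons given with each figure.

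The conclusion covers only what the protocol schedules. It assumes nothing about local practice. The estimand, sample size and primary analysis do not change.

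**What to change.** Either option closes the gap.

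**(a) Require 12 months.** Reword the FSH text in 10.4.1.2 so that postmenopausal status always needs at least 12 months of amenorrhea without another medical cause, and a high FSH may support that finding but not replace it. The reasoning in 8.3.6 then holds, and the Schedule of Activities needs no change. Cost: a few women in the menopausal transition, and HRT users of doubtful status who cannot meet the 12 months, become ineligible. The change also needs the usual amendment approvals under 10.1.1.

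**(b) Keep the route and test.** For women admitted on FSH without 12 months of amenorrhea, require a negative pregnancy test at screening and on Day -1 of each period. Amend 8.3.6 and the Schedule of Activities to match. A Day -1 test precedes all study radiation in that period, including the 57Co scan on Day 1 to Day 6 of Period 1. Cost: 1 + 2 = 3 simple tests per affected woman, plus the amendment. A Day -1 test can still miss a very recent conception, which is a reason to prefer (a).

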10.4.2. Contraception guidance

Female partners of childbearing potential with fertile male participants must use a highly effective contraceptive (see list below) plus participant use of a condom from the start of first study intervention until 90 days post-dose of last study intervention.

• CONTRACEPTIVES^a ALLOWED DURING THE STUDY INCLUDE:
• Highly Effective Methods^b That Have Low User Dependency Failure rate of <1% per year when used consistently and correctly.
Implantable progestogen-only hormone contraception associated with inhibition of ovulation ^c
Intrauterine device (IUD)
Intrauterine hormone-releasing system (IUS) ^c
Bilateral tubal occlusion/ligation
Azoospermic participant (vasectomized or due to a medical cause)

 • Azoospermia is a highly effective contraceptive method provided that the partner is the sole sexual partner of the WOCBP and the absence of sperm has been confirmed. If not, an additional highly effective method of contraception should be used. Spermatogenesis cycle is approximately 90 days. 
Note: documentation of azoospermia for a male participant can come from the site personnel's review of the participant's medical records, medical examination, or medical history interview.

• Highly Effective Methods^b That Are User Dependent Failure rate of <1% per year when used consistently and correctly.

Combined (estrogen- and progestogen-containing) hormonal contraception associated with inhibition of ovulation ^c 
 oral intravaginal transdermal injectable
Progestogen-only hormone contraception associated with inhibition of ovulation ^c 
 oral injectable
Sexual abstinence 
 Sexual abstinence is considered a highly effective method only if defined as refraining from heterosexual intercourse during the entire period of risk associated with the study intervention. The reliability of sexual abstinence needs to be evaluated in relation to the duration of the study and the preferred and usual lifestyle of the participant.

a. Contraceptive use by men or women should be consistent with local regulations regarding the use of contraceptive methods for those participating in clinical studies.
 
b. Failure rate of <1% per year when used consistently and correctly. Typical use failure rates differ from those when used consistently and correctly.
 
c. [Male condoms must be used in addition to hormonal contraception]. If locally required, in accordance with Clinical Trial Facilitation Group (CTFG) guidelines, acceptable contraceptive methods are limited to those which inhibit ovulation as the primary mode of action.
 
Note: Periodic abstinence (calendar, sympto-thermal, post-ovulation methods), withdrawal (coitus interruptus), spermicides only, and lactational amenorrhea method (LAM) are not acceptable methods of contraception. Male condom and female condom should not be used together (due to risk of failure from friction)

10.5. Appendix 5: Genetics

Not Applicable. Genetics are not evaluated in this study.

10.6. Appendix 6: Liver safety: suggested actions and follow-up assessments

Phase 1 Liver chemistry stopping criteria have been designed to assure participant safety and to evaluate liver event etiology.

Phase 1 Liver Chemistry Stopping Criteria and Required Follow Up Assessments

Liver Chemistry Stopping Criteria	
ALT-absolute	ALT \geq 3xULN If ALT \geq 3xULN AND total bilirubin \geq 2xULN (>35% direct bilirubin) or INR (if measured) >1.5, report as an SAE ^{1,2} .
Required Actions, Monitoring and Follow up Assessments	
Actions	Follow Up Assessments

 Immediately discontinue study intervention 	
 Viral hepatitis serology³

Liver Chemistry Stopping Criteria	

 Report the event to GSK within 24 hours Complete the liver event form and complete an SAE data collection tool if the event also meets the criteria for an SAE² Perform liver event follow up assessments as described in the Follow Up Assessment column Do not restart or rechallenge participant with study intervention Monitor the participant until liver chemistries resolve, stabilize, or return to within baseline (see MONITORING) 
MONITORING:
 
If ALT $\geq 3 \times \text{ULN}$ AND total bilirubin $\geq 2 \times \text{ULN}$ or INR > 1.5:
 
 Repeat liver chemistries (include ALT, aspartate transaminase [AST], alkaline phosphatase, total bilirubin and INR) and perform liver event follow up assessments within 24 hours Monitor participant twice weekly until liver chemistries resolve, stabilize or return to within baseline A specialist or hepatology consultation is recommended 
If ALT $\geq 3 \times \text{ULN}$ AND total bilirubin $< 2 \times \text{ULN}$ and INR ≤ 1.5:
 
 Perform liver chemistries (include ALT, AST, alkaline phosphatase, total bilirubin and INR) and perform liver event follow up assessments within 24-72 hours Monitor participant weekly until liver chemistries resolve, stabilize or return to within baseline 	
 Obtain INR and recheck with each liver chemistry assessment until the aminotransferases values show downward trend Obtain serum creatine phosphokinase (CPK) and lactate dehydrogenase (LDH), Fractionate bilirubin if total bilirubin $2 \times \text{ULN}$ Obtain complete blood count with differential to assess eosinophilia Record the appearance or worsening of clinical symptoms of liver injury, or hypersensitivity, on the liver event form Record use of concomitant medications on the concomitant medications report form including acetaminophen, herbal remedies, recreational drugs, and other over-the-counter medications Record alcohol use on the liver event alcohol intake form 
If ALT $\geq 3 \times \text{ULN}$ AND total bilirubin $\geq 2 \times \text{ULN}$ or INR > 1.5 obtain the following in addition to the assessments listed above:
 
 Anti-nuclear antibody, anti-smooth muscle antibody, Type 1 anti-liver kidney microsomal antibodies, and quantitative total immunoglobulin G (IgG) or gamma globulins Liver imaging (ultrasound, magnetic resonance, or computed tomography) and /or liver biopsy to evaluate liver disease, complete Liver Imaging form. Liver biopsy may be considered and discussed with local specialists if available, for instance:

Liver Chemistry Stopping Criteria	
	
 ○ In participants when serology raises the possibility of autoimmune hepatitis (AIH) ○ In participants when suspected DILI progresses or fails to resolve on withdrawal of study intervention ○ In participants with acute or chronic atypical presentation. ● If liver biopsy is conducted, then complete liver biopsy form

1. Serum bilirubin fractionation should be performed if testing is available. If serum bilirubin fractionation testing is unavailable, record the absence/presence of detectable urinary bilirubin on dipstick, which is indicative of direct bilirubin elevations suggesting liver injury.
2. All events of ALT $\geq 3 \times \text{ULN}$ and total bilirubin $2 \times \text{ULN}$ ($>35\%$ direct bilirubin) or ALT $3 \times \text{ULN}$ and INR >1.5 , which may indicate severe liver injury (possible 'Hy's Law'), must be reported as an SAE, the INR threshold value stated will not apply to participants receiving anticoagulants
3. Includes: hepatitis A immunoglobulin (IgM) antibody; HBsAg and HBcAb; hepatitis C RNA; cytomegalovirus IgM antibody; Epstein-Barr viral capsid antigen IgM antibody (or if unavailable, heterophile antibody or monospot testing) and hepatitis E IgM antibody.

10.7. **Appendix 7: Medical device AEs, ADEs, SAEs, sADEs, USADEs and device deficiencies: Definitions and procedures for recording, evaluating, follow-up, and reporting in medical device studies**

- The definitions and procedures detailed in this appendix are in accordance with ISO 14155 and the European MDR 2017/745 for clinical device research (if applicable).
- Both the investigator and the sponsor will comply with all local reporting requirements for medical devices.
- The detection and documentation procedures described in this protocol apply to all sponsor medical devices provided for use in the study. See Section 6.1.1 for the list of sponsor medical devices.

10.7.1. **Definition of medical device AE and ADE**

Medical device AE and ADE definition

 ● A medical device AE is any untoward medical occurrence, in a clinical study participant, users, or other persons, temporally associated with the use of study intervention whether or not considered related to the medical device. An AE can therefore be any unfavorable and unintended sign (including an abnormal laboratory finding), symptom, or disease (new or exacerbated) temporally associated with the use of a medical device. This definition includes events related to the medical device or comparator and events related to the procedures involved

except for events in users or other persons, which only include events related to devices.

- An ADE is defined as an AE related to the use of a medical device. This definition includes any AE resulting from insufficient or inadequate instructions for use or any malfunction of the medical device as well as any event resulting from use error or from intentional misuse of the medical device.

